Clinical Trial Protocol

Document Number:		c36040039-02
EudraCT No.	2021-003389-10	
BI Trial No.	1346-0017	
BI Investigational Medicinal Product	BI 425809	
Title	Effect of fluconazole on the pharmacokinetics of a single oral dose of BI 425809 in healthy male subjects (an open-label, two-period fixed-sequence design study)	
Lay Title	A study in healthy men to test how fluconazole influences the amount of BI 425809 in the blood	
Clinical Phase	I	
Clinical Trial Leader	

 Phone: + Fax: +	
Principal Investigator	

 Phone: + Fax: +	
Status	Final Protocol (Revised Protocol (based on global amendment 1))	
Version and Date	Version: 2.0	Date: 22 September 2021
Page 1 of 66		

Proprietary confidential information
 
© 2021 Boehringer Ingelheim International GmbH or one or more of its affiliated companies. All rights reserved. This document may not - in full or in part - be passed on, reproduced, published or otherwise used without prior written permission
		

CLINICAL TRIAL PROTOCOL SYNOPSIS

Company name	Boehringer Ingelheim
Protocol date	03 August 2021
Revision date	22 September 2021
BI trial number	1346-0017
Title of trial	Effect of fluconazole on the pharmacokinetics of a single oral dose of BI 425809 in healthy male subjects (an open-label, two-period fixed-sequence design study)
Principal Investigator	
Trial site	
Clinical phase	I
Trial rationale	Based on in vitro and in vivo data, CYP3A4 is involved in metabolism of BI 425809. It is therefore necessary to investigate whether co-administration of multiple doses of fluconazole, a moderate CYP3A inhibitor, affects single dose pharmacokinetics of BI 425809 in healthy male subjects
Trial objective	To investigate the effect of steady state exposure of fluconazole, a moderate CYP3A inhibitor, on the pharmacokinetics of BI 425809 in healthy subjects
Trial design	Open-label, two-period fixed-sequence trial with 2 treatments (R and T)
Trial endpoints:	Primary endpoints: AUC _{0-215h} and C _{max} of BI 425809 Secondary endpoint: AUC _{0-∞} of BI 425809
Number of subjects total entered each treatment	15 15
Diagnosis	Not applicable
Main criteria for inclusion	Healthy male subjects, age of 18 to 55 years (inclusive), body mass index (BMI) of 18.5 to 29.9 kg/m ² (inclusive)
Trial product 1 dose mode of admin.	BI 425809, 10 mg film-coated tablets 10 mg in Treatment Test and in Treatment Reference Oral with 240 mL of water after an overnight fast of at least 10 h

Trial product 2	Fluconazole, 200 mg hard capsules
dose	2x 200 mg (= 400 mg fluconazole) once daily during Treatment Test, only
mode of admin.	Oral with 240 mL of water
Duration of treatment	
Treatment Reference: BI 425809, single dose
 
Treatment Test: 2 capsules with 200 mg fluconazole (=400 mg) qd on study day -4 until study day +9 (total of 13 dosing days); on study day 1, BI 425809 (as single dose) will be administered 1 hour after fluconazole
 
The BI 425809 single doses of Treatments Reference and Test will be separated by a wash-out period of at least 16 days.

Statistical methods	
The effect of fluconazole on the pharmacokinetics of BI 425809 will be estimated by the ratios of the geometric means (test/reference) for the primary and secondary endpoints. Additionally, their two-sided 90% confidence intervals (CIs) will be provided. This method corresponds to the two one-sided t-test procedure, each at a 5% significance level. Since the main focus is on estimation and not testing, a formal hypothesis test and associated acceptance range is not specified. The statistical model will be an analysis of variance (ANOVA) on the logarithmic scale including effects for 'subject' and 'treatment'. CIs will be calculated based on the residual error from the ANOVA.
 
Descriptive statistics will be calculated for all endpoints.

FLOW CHART

Period	Visit	Day	Planned time (relative to BI 425809 administration [h:min])	Approximate clock time of actual day [h:min]	Event and comment	Safety laboratory ⁸	PK plasma (BI 425809)	PK plasma (fluconazole)	12-lead ECG	Vital signs (BP, PR)	Questioning for AEs and concomitant therapy ⁵
SCR	1	-21 to -1			Screening (SCR) ¹	A			x	x	
Treatment R (BI 425809 single dose)	2	1	-2:00	07:00	Admission to trial site	B ^{2,9}	x ²	x ²	x ²	x ²	x ²
			-1:00	08:00	240 mL fluid intake						
			0:00	09:00	Administration of BI 425809						
			0:30	09:30			x				
			1:00	10:00			x				
			1:30	10:30			x				
			2:00	11:00	240 mL fluid intake		x				x
			3:00	12:00			x				
			4:00	13:00	240 mL fluid intake, Lunch ³		x				x
			5:00	14:00			x				
			6:00	15:00			x				
			7:00	16:00	Light snack (voluntary)						
			8:00	17:00			x				
			10:00	19:00	Dinner						
			12:00	21:00			x				x
	2		24:00	09:00	Breakfast (voluntary) ³ , discharge from trial site	B	x				x
	3		47:00	08:00	Ambulatory visit		x				x
	4		71:00	08:00	Ambulatory visit		x				x
	6		119:00	08:00	Ambulatory visit		x				x
	8		167:00	08:00	Ambulatory visit		x				x
	10		215:00	08:00	Ambulatory visit	C	x				x

- Subject must be informed and written informed consent obtained prior to starting any screening procedures. Screening procedures include physical examination, check of vital signs, ECG, safety laboratory (including drug screening), demographics (including determination of body height and weight, smoking status and alcohol history), relevant medical history, concomitant therapy and review of inclusion/exclusion criteria. Pharmacogenetic samples will be collected if needed.
- The time is approximate; the procedure is to be performed and completed within the 3 h prior to BI 425809 drug administration.
- If several actions are indicated at the same time, the intake of meals will be the last action.
- See [Flow Chart \(cont.\)](#) on next page
- AEs and concomitant therapies will be recorded throughout the trial, but will be specifically asked for at the times indicated in the [Flow Chart](#) above.
- Only applicable for Flow Chart for Treatment T
- Only applicable for Flow Chart for Treatment T
- Letters A, B, C and D (in Flow Chart below) define different sets of safety laboratory examinations (for details refer to Section [5.2.3](#)).
- Including urine drug screening and alcohol breath test

FLOW CHART (cont.)

[figure not shown]
Period	Visit	Day	Planned time (relative to BI 425809 administration) [h:min]	Approximate clock time of actual day [h:min]	Event and comment	Safety laboratory ⁸	PK plasma (BI 425809)	PK plasma (fluconazole)	12-lead ECG	Vital signs (BP, PR)	Questioning for AEs and concomitant therapy ⁵
Treatment T (Fluconazole multiple dose + BI 425809 single dose)	3	-4	-97:00	08:00	Fluconazole administration				x		x
		-3	-73:00	08:00	Fluconazole administration						x
		-2	-49:00	08:00	Fluconazole administration						x
		-1	-25:00	08:00	Fluconazole administration	C					x
		1	-2:00	07:00	Admission to trial site	B ^{2,9}	x ²		x ²	x ²	x ²
			-1:00	08:00	Fluconazole administration			x ⁷			
			0:00	09:00	Administration of BI 425809						
			0:30	09:30			x				
			1:00	10:00			x				
			1:30	10:30			x				
			2:00	11:00	240 mL fluid intake		x				
			3:00	12:00			x			x	
			4:00	13:00	240 mL fluid intake, Lunch ³		x				x
			5:00	14:00			x				
			6:00	15:00			x				
			7:00	16:00	Light snack (voluntary)						
			8:00	17:00			x				x
			10:00	19:00	Dinner						
			12:00	21:00			x				x
		2	23:00	08:00	Fluconazole administration			x ⁷			x
			24:00	09:00	Breakfast (voluntary) ³ , discharge from trial site	B	x		x	x	x
		3	47:00	08:00	Fluconazole administration ⁶		x	x			x
		4	71:00	08:00	Fluconazole administration ⁶	C	x				x
		5	95:00	08:00	Fluconazole administration						x
		6	119:00	08:00	Fluconazole administration ⁶	C	x				x
		7	143:00	08:00	Fluconazole administration						x
		8	167:00	08:00	Fluconazole administration ⁶	C	x		x		x
		9	191:00	08:00	Fluconazole administration						x
		10	215:00	08:00	Ambulatory visit		x				x
FU	4	16 to 30			End of trial (EoTrial) examination ⁴	D			x	x	x

1. See [Flow Chart](#) on previous page.
2. The time is approximate; the procedure is to be performed and completed within the 2 h prior to fluconazole drug administration.
3. If several actions are indicated at the same time, the intake of meals will be the last action.
4. At the end of trial visit the EoTrial examination includes physical examination, vital signs, ECG, safety laboratory, recording of AEs and concomitant therapies.
5. AEs and concomitant therapies will be recorded throughout the trial, but will be specifically asked for at the times indicated in the Flow Chart above.
6. Immediately after PK blood sampling.
7. PK sampling pre-dose (tolerance with respect to planned time: -5 min); fluconazole administration on time.
8. Letters A, B, C and D define different sets of safety laboratory examinations (for details refer to Section [5.2.3](#)).
9. Including urine drug screening and alcohol breath test

TABLE OF CONTENTS

TITLE PAGE	1
CLINICAL TRIAL PROTOCOL SYNOPSIS	2
FLOW CHART	4
TABLE OF CONTENTS	6
ABBREVIATIONS	10
1. INTRODUCTION.....	13
1.1 MEDICAL BACKGROUND	13
1.2 DRUG PROFILE	13
1.2.1 BI 425809	13
1.2.1.1 Non-clinical drug safety.....	13
1.2.1.2 Clinical Safety in Healthy Subjects	14
1.2.1.3 Expected exposure of BI 425809 in this trial.....	15
1.2.2 Fluconazole	16
1.2.3 Residual Effect Period	19
1.3 RATIONALE FOR PERFORMING THE TRIAL	19
1.4 BENEFIT - RISK ASSESSMENT	19
1.4.1 Expected benefit for the target population	19
1.4.2 Procedure-related risks	20
1.4.3 Drug-related risks and safety measures.....	20
1.4.3.1 Risks related to the administration of BI 425809	20
1.4.3.2 Risks related to the administration of fluconazole.....	21
1.4.3.3 Drug-induced liver injury	22

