1.4.3.2 Risks related to the administration of fluconazole

Fluconazole (Diflucan[®]) is a market-approved drug. The dose used in this trial (400 mg qd for 13 days) is within the therapeutic range used for patients to treat fungal infections [[R21-2282](#)].

Based on the German ‘Fachinformation’ for Diflucan[®], the following adverse reactions have been observed and reported during treatment with Diflucan with the following frequencies: Very common ($\geq 1/10$); common ($\geq 1/100$ to $< 1/10$); uncommon ($\geq 1/1,000$ to $< 1/100$); rare ($\geq 1/10,000$ to $< 1/1,000$); very rare ($< 1/10,000$), not known (cannot be estimated from the available data).

- Common: Headache, abdominal pain, vomiting, diarrhea, nausea, alanine aminotransferase increased, aspartate aminotransferase increased, blood alkaline phosphatase increased, rash
- Uncommon: Anaemia, decreased appetite, somnolence, insomnia, seizures, paraesthesia, dizziness, taste perversion, vertigo, constipation, dyspepsia, flatulence, dry mouth, cholestasis, jaundice, bilirubin increased, drug eruption, urticarial, pruritus, increased sweating, myalgia, fatigue, malaise, asthenia, fever
- Rare: Agranulocytosis, leukopenia, thrombocytopenia, neutropenia, anaphylaxis, hypercholesterolaemia, hypertriglyceridaemia, hypokalemia, tremor, torsade de pointes, QT prolongation, hepatic failure, hepatocellular necrosis, hepatitis, hepatocellular damage, toxic epidermal necrolysis, Stevens-Johnson syndrome, acute generalized exanthematous-pustulosis, dermatitis exfoliative, angioedema, face oedema, alopecia
- Not known: Drug reaction with eosinophilia and systemic symptoms (DRESS)

Risk mitigation hepatic injury:

- During fluconazole dosing phase laboratory liver parameters will be regularly assessed
- Only subjects with liver parameters AST, ALT and GGT within normal range will be allowed to participate in the trial (see Section [3.3.3](#))
- In case of relevant increase in liver enzymes or hepatic injury (DILI), subjects will discontinue trial treatment (see Section [3.3.4.1](#))

Risk mitigation QT prolongation:

- Subjects with baseline disease (such as pro-arrhythmic conditions) will be excluded from the trial
- No concomitant therapy prolonging the QT interval will be allowed
- During fluconazole dosing phase ECG will be assessed regularly for potential QT prolongation
- Laboratory tests (including determination of potassium levels) will be performed

Risk mitigation dermatological reaction:

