3.3.4.1 Discontinuation of trial treatment

An individual subject will discontinue trial treatment if:

1. The subject wants to discontinue trial treatment, without the need to justify the decision
2. The subject has repeatedly shown to be non-compliant with important trial procedures and, in the opinion of both, the investigator and sponsor representative, is not willing or able to adhere to the trial requirements in the future.
3. The subject needs to take concomitant medication that interferes with the investigational medicinal product or other trial treatment
4. The subject can no longer receive trial treatment for medical reasons (such as surgery, adverse events [AEs], or diseases)
5. The subject has an elevation of AST and/or ALT ≥ 3 -fold ULN
6. The subject has an elevation of AST and/or ALT ≥ 1.5 -fold ULN and a control blood sample, which will be withdrawn on the next day, confirms further meaningful increase of the respective parameter. It is with the investigator to evaluate the clinical significance of this increase taking into account its occurrence in relation to the 13 days of fluconazole treatment
7. The subject has an elevation of AST and/or ALT ≥ 3 -fold ULN and an elevation of total bilirubin ≥ 2 -fold ULN (measured in the same blood sample) and/or needs to be followed up according to the DILI checklist provided in the ISF
8. In case a rash occurs during the fluconazole dosing phase which is attributable to fluconazole treatment, the respective subject will discontinue study treatment

In addition to these criteria, the investigator may discontinue subjects at any time based on his or her clinical judgment.

Even if the trial treatment is discontinued, the subject remains in the trial and, given his/her agreement, will undergo the procedures for early treatment discontinuation and follow up as outlined in the [Flow Chart](#) and Section [6.2.3](#).

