6. INVESTIGATIONAL PLAN

6.1 VISIT SCHEDULE

Exact times of measurements outside the permitted time windows will be documented. The acceptable time windows for screening and the end of trial examination are provided in the [Flow Chart](#).

Study measurements and assessments scheduled to occur 'before' BI 425809 administration on Day 1 are to be performed and completed within a 3 h-period prior administration of BI 425809.

In ambulatory visits prior to administration of BI 425809 in period 2, the acceptable deviation from the scheduled time for ECG and laboratory tests will be -15 min.

Following administration of BI 425809, the acceptable deviation from the scheduled time for vital signs, ECG, and laboratory tests will be ± 45 min until Day 6. From Day 8 onwards, a deviation from the scheduled time for fluconazole administration, safety laboratory tests, and ECG of ± 60 min is acceptable.

If scheduled in the Flow Chart at the same time as a meal, blood sampling, vital signs, and 12-lead ECG recordings have to be done first. 12-lead ECG measurements should always be the first procedure. Furthermore, if several measurements including venepuncture are scheduled for the same time, venepuncture should be the last of the measurements due to its inconvenience to the subject and possible influence on physiological parameters.

For planned blood sampling times, refer to the Flow Chart. While these nominal times should be adhered to as closely as possible, the actual sampling times will be recorded and used for the determination of pharmacokinetic parameters.

If a subject misses an appointment, it will be rescheduled if possible. The relevance of measurements outside the permitted time windows will be assessed no later than at the Report Planning Meeting.

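### In the Test period the last scheduled on-treatment total bilirubin is on Day 2 of a fluconazole course that runs to Day 9; adding bilirubin to safety laboratory set C closes most of the gap at little cost

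*Protocol*

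**What the plan says.** Footnote 8 of the protocol Flow Chart (cont.) explains the laboratory column: "Letters A, B, C and D define different sets of safety laboratory examinations". For Treatment T the Flow Chart schedules these sets as follows: C on Day -1, B on Day 1 before dosing, B on Day 2, and C on Days 4, 6 and 8. Day 10 (215:00) is listed as "Ambulatory visit" with a BI 425809 blood sample, but its laboratory cell is empty. The next laboratory set is D, at the "End of trial (EoTrial) examination" on Day 16 to 30.

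Table 5.2.3: 1 places AST, ALT, alkaline phosphatase and GGT in all four sets. Total bilirubin is in A, B and D but not in C. Section 5.2.3 exempts set C from fasting.

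Fluconazole is given once daily from Day -4 to Day 9. Section 1.4.3.2 lists among its common reactions "alanine aminotransferase increased, aspartate aminotransferase increased, blood alkaline phosphatase increased, rash". As mitigation it says: "During fluconazole dosing phase laboratory liver parameters will be regularly assessed".

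Section 5.2.5.1.4 defines hepatic injury, an adverse event of special interest (AESI), in two ways. The first is AST/ALT of at least 3-fold ULN with total bilirubin of at least 2-fold ULN in one sample. The second is AST/ALT of at least 10-fold ULN. Section 3.3.4.1, item 7, repeats the paired criterion, with the values "measured in the same blood sample) and/or needs to be followed up according to the DILI checklist provided in the ISF". Item 5 of that section stops treatment at AST/ALT of at least 3-fold ULN alone.

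On the analysis side, SAP Table 6.1: 1 ends the Test on-treatment phase 14 days after the second BI 425809 dose. SAP 6.7 takes the last value before BI 425809 as baseline. SAP 7.8.2 plans a shift table from baseline to the last on-treatment value.

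**The concern.** The paired criterion needs enzymes and bilirubin from the same sample, yet the panel used for all monitoring after Day 2 contains only the enzymes. If AST or ALT reached 3-fold ULN on Day 4, 6 or 8, the scheduled sample alone could not show whether the first hepatic-injury definition was met. That definition matters because it carries reporting in the SAE timeframe. Bilirubin would have to come from an add-on test, a repeat sample or the early end-of-trial visit.

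A descriptive consequence follows. Absent unscheduled tests, the bilirubin shift table for Test says nothing about the later part of the fluconazole course.

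A smaller point concerns the end of dosing. The last scheduled enzymes are on Day 8, and no scheduled on-treatment panel follows the complete course. Reference Day 10, after a single dose of BI 425809 alone, does carry set C.

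**Working it through.** **Dose count (the plan's own figure).** There is no Day 0. Days -4 to -1 give 4 doses and Days 1 to 9 give 9; 4 + 9 = 13, which matches the stated 13 dosing days.

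**Doses before the last bilirubin.** Set B on Day 2 is at 09:00, one hour after that day's fluconazole. Doses given: 4 + 2 = 6. Doses still to come: 13 - 6 = 7.

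**Doses before the last enzymes.** Footnote 6 of the Flow Chart places the Day 8 dose "Immediately after PK blood sampling", so the Day 8 panel nominally follows 4 + 7 = 11 doses. The count is nominal because Section 6.1 allows "From Day 8 onwards, a deviation from the scheduled time for fluconazole administration, safety laboratory tests, and ECG" of up to 60 minutes either way. A sample taken after the Day 8 dose would follow 12.

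**End of the on-treatment phase.** Day 1 09:00 + 14 days = Day 15 09:00. As a check, the last fluconazole dose plus its 6-day residual effect period is Day 9 08:00 + 6 days = Day 15 08:00, which reproduces the one-hour difference stated in SAP 6.1. The end-of-trial visit opens on Day 16, so its set D falls in follow-up.

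**Span of the bilirubin shift table.** Baseline in Test is the Day 1 pre-dose sample, nominally at 07:00 and already after 4 fluconazole doses. The last scheduled on-treatment value is Day 2 09:00. The span is 26 hours.

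**Schedule now and with each change (Test period).**

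| | Now | Bilirubin in set C | Plus set C on Day 10 |
|---|---|---|---|
| Enzyme panels | 6 | 6 | 7 |
| Panels with enzymes and bilirubin | 2 of 6 | 6 of 6 | 7 of 7 |
| Last enzymes before end of trial | Day 8 | Day 8 | Day 10 |
| Last on-treatment bilirubin | Day 2 | Day 8 | Day 10 |
| Doses after last enzymes (nominal) | 13 - 11 = 2 | 2 | 0 |
| Doses after last bilirubin (nominal) | 7 | 2 | 0 |
| Gap, enzymes to end of trial (days) | 16 - 8 = 8 to 30 - 8 = 22 | 8 to 22 | 16 - 10 = 6 to 30 - 10 = 20 |
| Gap, bilirubin to end of trial (days) | 16 - 2 = 14 to 30 - 2 = 28 | 8 to 22 | 6 to 20 |

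After Day 2, the scheduled panels that contain bilirubin number 0 of 3 now.

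**The case against.** The strongest reply is that nothing is broken and this is a preference for more sampling. Much of that stands.

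- A reader might infer that the protocol fails its own liver-monitoring commitment. It does not. Section 1.4.3.2 promises regular assessment during fluconazole dosing and names neither days nor bilirubin; six Test panels meet it.
- A reader might infer that a subject with liver injury could stay on fluconazole because bilirubin is missing. The documents do not support that. Item 5 stops treatment on the enzymes alone and wholly contains the laboratory limb of item 7. Item 6 adds a next-day control sample from 1.5-fold ULN.
- A reader might infer that the AESI could not be classified at all. The protocol has a route. Under Sections 3.3.4.1 and 6.2.3, subjects who stop treatment early should have the end-of-trial visit, and set D measures enzymes and bilirubin together. The 10-fold definition needs no bilirubin. Section 5.2.5.1.4 also requires bilirubin, unscheduled if necessary, when symptoms suggest liver injury and results are lacking. The DILI checklist may ask for more, but it is in the investigator site file and not public.
- A reader might take the empty Day 10 cell as an oversight, given set C on Reference Day 10. The documents do not settle this. The schedule may be deliberate, and the BI 425809 risk and residual-effect sections are redacted.

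What survives is narrower. The early-stop visit has no stated day, so it does not guarantee bilirubin from the sample that raised the alarm. These other routes also need a prior signal or a symptom. The shift-table effect is descriptive only, since all individual values are listed, including those from the end of trial.

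**Conclusion.** The point holds as a cheap improvement for the sponsor to consider. Scheduled Test monitoring after Day 2 cannot by itself assess the protocol's paired enzyme and bilirubin criterion, and 7 of 13 fluconazole doses nominally follow the last scheduled on-treatment bilirubin. No pharmacokinetic endpoint, eligibility rule or stopping rule is affected.

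The two parts differ in value. Bilirubin in set C is the stronger one: it lets every scheduled enzyme panel assess the paired criterion and carries the bilirubin shift table through the period of repeated dosing. The Day 10 panel is secondary. Its result comes after the last dose, so it can inform detection, attribution and follow-up but not dosing, and 6 to 20 days to the end of trial remain. The documents give no rate of first enzyme rises between Day 8 and Day 10, so no yield is claimed.

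The counts assume nominal sampling times, no unscheduled tests, and an end-of-trial window counted from Day 1 of the Test period. The schedule facts are certain; the size of the benefit is not.

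**What to change.** **Main change.** Add total bilirubin to set C in Table 5.2.3: 1. This is one extra analyte and one table edit. Over the existing set C draws (Reference Day 10 and Test Days -1, 4, 6 and 8) it means 5 x 15 = 75 analyses.

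**Secondary change.** Add set C to the Test Day 10 (215:00) row of the Flow Chart, drawn at the BI 425809 venepuncture already scheduled. Set C needs no fasting. This takes one extra tube per subject, 15 in all, with no new visit. Bilirubin analyses then total 6 x 15 = 90 across both periods, or 4 x 15 = 60 if bilirubin is added only on Test Days 4, 6, 8 and 10.

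The tube volume is not stated and counts towards the 500 mL ceiling in Section 1.4.2. Pharmacokinetic and genotyping blood uses about 34 x 2.7 + 4 x 2.7 + 10 = 112.6 mL of that; safety laboratory volumes are not given. The planned SAP analysis needs no change.
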